In this study, the aim is to release the brake on the immune response by use of nivolumab, an inhibitory antibody against PD-1. Importantly, the immune response may not only boost local tumor control, but lead to eradication of metastatic disease and hence bring patients to a curative situation. Nivolumab has previously been shown to be effective in phase III trials in melanoma, lung cancer and renal cell carcinoma. Recently the results from a phase III study in HNSCC was reported(3). This was, an open-label, randomized study of nivolumab versus investigator’s choice of therapy in previously treated patients with HNSCC. The patients had tumor progression on or within 6 months of platinum therapy in the primary, recurrent, or metastatic setting. The trial randomized 361 patients 2:1 to receive either nivolumab 3 mg/kg intravenously every two weeks or investigator’s choice (cetuximab/methotrexate/docetaxel) until documented disease progression or unacceptable toxicity. The primary endpoint was OS. The study was stopped early due to positive interim results in favour of nivolumab. At the interim analysis, which was conducted after 218 events, patients assigned to nivolumab were found to have a 30 percent reduction in risk of death compared with those assigned therapy of investigator’s choice. Median overall survival was 7.5 months for those assigned nivolumab versus 5.1 months for those assigned therapy of investigator’s choice. At 12 months, 36 percent of the patients treated with nivolumab were alive compared with 17 percent of those assigned therapy of investigator’s choice. The response rate was 13.3% in the nivolumab group versus 5.8% in the standard-therapy group. The safety profile for nivolumab was favorable compared to the investigator’s choice therapy, and consistent with prior studies. Treatment-related adverse events of grade 3 or 4 occurred in 13.1% of the patients in the nivolumab group versus 35.1% of those in the standard-therapy group

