3.0 SAFETY MONITORING COMMITTEE

A safety monitoring committee (SMC) will monitor safety on a periodic basis. Members of the

SMC will be experienced clinicians. The SMC will meet approximately every 6 months from the point of first patient in (FPI) to review safety and study conduct data. The safety data will include demographic data, adverse events and relevant laboratory data. In addition the SMC will meet after finalization of each dose cohort (i.e. three patients has completed minimum 8 weeks of treatment), and in case DLT is experienced. See section 8.8 for definitions.

Following each data review, the SMC will provide recommendations to the Study Leadership as to whether the study should continue or be amended, or whether the study should be stopped on the basis of safety (i.e., evidence of harm). The Study Leadership will make a decision on the basis of the SMC recommendations.

Any outcomes of these safety reviews that affect study conduct will be communicated in a timely manner to the investigators for notification of the Institutional Review Boards/Ethics Committees (IRBs/ECs).

No interim efficacy analysis is planned.

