5.3.2.1 Dose Delay Criteria for Nivolumab

Dose delay criteria apply for all drug-related AEs. A treatment delay up to 4 weeks, i.e. 6 weeks calculated from the last dose, is allowed. A treatment delay beyond this must be discussed with the Study leadership. A treatment delay beyond 10 weeks is not allowed.

Tumor assessments should continue per protocol schedule, even if dosing is delayed.

Nivolumab administration should be delayed for the following reasons:

- Any Grade ≥ 2 non-skin drug-related adverse event, except for fatigue and laboratory abnormalities
- Any Grade 3 skin drug-related adverse event
- Any Grade 3 drug-related laboratory abnormality
- Any adverse event, laboratory abnormality, intercurrent illness or other reason which, in the judgment of the investigator, warrants delaying the dose of study medication.

Subjects who require delay of nivolumab should be re-evaluated weekly or more frequently if clinically indicated. Nivolumab dosing can be resumed on the established dosing schedule when retreatment criteria are met (Section 5.3.2.2).

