5.6 Clinical Criteria for Early Trial Termination

Early trial termination will be the result of the criteria specified below:

1. Quality or quantity of data recording is inaccurate or incomplete
2. Poor adherence to protocol and regulatory requirements
3. Incidence or severity of adverse drug reaction in this or other studies indicates a potential health hazard to subjects
4. Plans to modify or discontinue the development of the study drug

In the event of BMS decision to no longer supply study drug, ample notification will be provided so that appropriate adjustments to subject treatment can be made.

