9.2.1 Serious Adverse Event Collection and Reporting

The Investigator Brochure (IB) represents the Reference Safety Information to determine expectedness of serious adverse events for expedited reporting. Following the subject's written consent to participate in the study, all SAEs, whether related or not related to study drug, must be collected, including those thought to be associated with protocol-specified procedures. All SAEs must be collected that occur during the screening period and within 90 days of the last dose of nivolumab. If applicable, SAEs must be collected that relate to any later protocol-specified procedure (eg, a follow-up skin biopsy). For subjects included and never treated with study drug, SAEs should be collected for 30 days from the date of inclusion.

The investigator must report any SAE that occurs after these time periods and that is believed to be related to study drug or protocol-specified procedure.

An SAE report must be completed for any event where doubt exists regarding its seriousness.

If the investigator believes that an SAE is not related to study drug, but is potentially related to the conditions of the study (such as withdrawal of previous therapy or a complication of a study procedure), the relationship must be specified in the narrative section of the SAE Report Form.

SAEs, whether related or not related to study drug, and pregnancies, must be reported to Sponsor (or designee) within 24 hours of awareness of the event. SAEs must be recorded on the SAE Report Form; pregnancies on a Pregnancy Surveillance Form (electronic or paper forms).

If only limited information is initially available, follow-up reports are required.

If an ongoing SAE changes in its intensity or relationship to study drug or if new information becomes available, the SAE report must be updated and submitted within 24 hours to Sponsor (or designee) using the same procedure used for transmitting the initial SAE report.

All SAEs must be followed to resolution or stabilization.

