9.8 Dose Limited Toxicity (DLT)

We foresee that DLT related to Grade 3 and/or 4 dermatitis and mucositis may be experienced.

During dose escalation phase: If a patient experience a possibly nivolumab-related Grade 3 adverse event at any dose level, an additional patient will be included at this dose level. If one more patient experience the same Grade 3 event on the same dose level (i.e. 2 of 4 patients at one dose level experiences the same Grade 3 event), this will be defined as DLT reached, and the dose should be reduced by one level. If DLT is experienced at the lowest dose level (1,0 mg/kg), the dose will be reduced to 0.3 mg/kg. If two patients experience DLT at this dose level, the study will be terminated. If a patient experiences a Grade 4 event, the dose should immediately be reduced by one level.

The Safety Monitoring Committee (SMC) will meet in the case of DLT, to discuss further progress related to doses of nivolumab, and whether the protocol should be amended. In

addition, the SMC will meet after every time three patients have completed each dose level (i.e. completed the re-radiation), to discuss whether it will be safe to move to next dose level. No further patients will be included until the SMC has met. After the dose escalation phase has been completed, the SMC will meet if two patients experience AE grade 3 or one patient experiences AE Grade 4, considered related to nivolumab. No further patients will be included until the SMC has met.

The SMC is a group of oncologists located at the Clinical Cancer Research Unit, with experience in immunotherapy treatment. The members will not be involved in the study design or the study treatment.

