9.9.1 Evaluating Adverse Events

An Investigator who is a qualified physician will evaluate all adverse events according to the NCI Common Terminology for Adverse Events (CTCAE), version 4.0. Any adverse event which changes CTCAE grade over the course of a given episode will have each change of grade recorded on the adverse event case report forms/worksheets.

All adverse events regardless of CTCAE grade must also be evaluated for seriousness.

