9.10 Sponsor Responsibility for Reporting Adverse Events

All Adverse Events will be reported to Competent Authorities and Investigators in accordance with applicable national laws and regulations.

Suspected Unexpected Serious Adverse Reactions (SUSARs) will be reported to the Competent Authority according to national regulation. The following timelines should be followed:

The sponsor will ensure that all relevant information about SUSARs that are fatal or life-threatening is recorded and reported as soon as possible to the Competent Authority concerned in any case no later than seven (7) days after knowledge by the sponsor of such a case, and that relevant follow-up information is subsequently communicated within an additional eight (8) days.

All other SUSARs will be reported to the Competent Authority concerned as soon as possible but within a maximum of fifteen (15) days of first knowledge by the sponsor.

SUSARs will be reported using the CIOMS form since Oslo University Hospital (sponsor) is not connected to EudraVigilance.

10.0 COLLATERAL RESEARCH.

An extensive research program will be conducted. The patient informed consent form will allow for performing biomarker analyses, immunological studies, gene profiling and studies of tumor evolution/heterogeneity during treatment, as well as comparison with data/material from other studies.

10.1 Biobanking:

Please see the study flow chart for information on the time points for collection of biopsies and peripheral blood.

- Tumor biopsies collected pre, during and post therapy (time of progression). If sufficient tissue is available, the tumor will be cut into two/three pieces:
 - Fresh tumor cells/ tumor infiltrating lymphocytes frozen as cell suspension for CYTOF/flow cytometry, analysis of T cell specificity with multimers and functional immune assays
 - Snap-frozen tumor biopsies
 - FFPE tissue
- Peripheral blood samples collected pre-, during and post-therapy:
 - Peripheral blood mononuclear cells, processed with gradient centrifugation and frozen on liquid nitrogen
 - Plasma/serum, separated and frozen.

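### After dose escalation, the rule in 9.8 that convenes the SMC and holds inclusion names related Grade 3 and Grade 4 events but not Grade 5, so read literally a sudden related death triggers neither

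*Combined protocol and SAP*

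**What the plan says.** Section 9.8 (Dose Limited Toxicity) sets the post-escalation rule: "the SMC will meet if two patients experience AE grade 3 or one patient experiences AE Grade 4, considered related to nivolumab". The next sentence stops inclusion until the SMC has met. The hold therefore depends on this trigger and has none of its own. The escalation rules in the same section also name Grades 3 and 4 only.

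Section 3.0 adds routine SMC meetings about every six months from first patient in, a meeting after each dose cohort, and a meeting in case of DLT. For the definition of DLT it refers to the DLT section, which does not mention Grade 5 or death.

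A death is dealt with elsewhere:

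- Section 9.2.1: serious adverse events "must be reported to Sponsor (or designee) within 24 hours of awareness of the event".
- Section 9.10: a fatal or life-threatening SUSAR goes to the Competent Authority "no later than seven (7) days after knowledge by the sponsor of such a case".
- Section 5.6: one of the criteria that lead to early termination is "Incidence or severity of adverse drug reaction in this or other studies indicates a potential health hazard to subjects".
- Section 9.9.1: "Any adverse event which changes CTCAE grade over the course of a given episode will have each change of grade recorded".

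**The concern.** The rule ranks outcomes in the wrong order for one kind of event. A single related Grade 4 event that the patient survives convenes the SMC and stops inclusion. A related death that is sudden, or that follows directly from a low grade, does neither by itself.

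This matters most after escalation. If no patient is added to a dose level, 14 of the 20 patients are treated in that phase. The six-week stagger and the cohort reviews are then over, and the 9.8 trigger is the only rule that automatically stops inclusion between routine meetings. Section 2.1 itself says that the combination has hardly been studied in humans and that re-irradiation carries serious acute and late toxicity. What is at stake is that further patients could start treatment after a related death without prior SMC review.

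**Working it through.** The plan gives no figure for this rule, so there is none to reproduce. The check has a textual part and a conditional size.

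**1. The rule applied to one related fatal event after escalation**

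| Course recorded before death | Trigger met? |
|---|---|
| A related Grade 4 stage | Yes, by the Grade 4 arm (9.9.1 has the change of grade recorded) |
| A related Grade 3 stage, second such patient | Yes, by the Grade 3 arm |
| A related Grade 3 stage, first such patient | No |
| Neither stage (sudden death, or jump from a lower grade) | No |

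Reporting under 9.2.1 and 9.10 informs the sponsor and the authority. Section 5.6 provides for termination. None of the three requires an SMC meeting or holds inclusion.

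**2. Inputs for the size**

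- Patients after escalation: 20 − 2 × 3 = 14 (Section 5.2).
- Enrolment Q2 2017 to Q4 2018 (Section 1.0): at most 21 months, or 91 weeks.
- Escalation, with starts six weeks apart (5.2): each cohort's third patient starts 12 weeks after its first. With review after 8 weeks of treatment (3.0), escalation takes 2 × (12 + 8) = 40 weeks. With review after re-irradiation ends (9.8), which is 2 + 4 = 6 weeks after the first dose, it takes 2 × (12 + 6) = 36 weeks.
- Weeks left for accrual: W = 91 − 40 = 51, or 91 − 36 = 55.
- Even accrual (assumed): r = 14/51 = 0.275 or 14/55 = 0.255 patients per week.
- Assumed throughout: no other trigger fires and the sponsor takes no action.

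**3. Upper bound.** A death just after a routine meeting leaves 26 weeks to the next: 26r = 7.1 or 6.6 further starts.

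**4. Average, with the wait to the next meeting uniform over 0–26 weeks and starts ending at patient 20.** For a death uniform over post-escalation accrual, the mean is r × (13 − 26²/(6W)):

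- W = 51: 0.2745 × (13 − 2.209) = 2.96
- W = 55: 0.2545 × (13 − 2.048) = 2.79

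**5. Average, with meetings fixed at weeks 26, 52 and 78 from first patient in, as Section 3.0 implies.** Post-escalation accrual is cut into pieces of length d by the meetings and by week 91. The mean is r × Σd²/(2W):

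- From week 40: 0.2745 × (12² + 26² + 13²)/102 = 0.2745 × 9.696 = 2.66
- From week 36: 0.2545 × (16² + 26² + 13²)/110 = 0.2545 × 10.009 = 2.55

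**6. Other death timings (by simulation, 4 million draws, week-40 and week-36 cases).**

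| Timing of death | Random wait | Meetings from first patient in |
|---|---|---|
| Uniform over post-escalation accrual | 2.96 / 2.79 | 2.66 / 2.55 |
| Within 8 weeks of a patient's start | 2.68 / 2.55 | 2.46 / 2.30 |
| Any time in 12 months after start | 1.23 / 1.26 | 1.12 / 1.15 |

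The last row is low because about half of such deaths (51% or 47%) fall after accrual has ended. Slower accrual lowers all these figures, and a shorter enrolment window raises them.

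**The case against.** The strongest reply is that nobody would read the rule this way. Grade 4 works as the top of the scale throughout this protocol. The discontinuation criteria (5.3.2.3) and the infusion-reaction rules (5.3.2.6) also stop at Grade 4, and no one would take the latter to exempt a fatal infusion reaction. That stands, and Grade 4 or worse is very likely the intent.

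It also disposes of a tempting stronger reading. Section 5.3.2.1 writes a floor explicitly, "Any Grade ≥ 2 non-skin drug-related adverse event, except for fatigue and laboratory abnormalities", and a reader might infer that the bare grade in 9.8 was meant to leave deaths out. Drafting practice across the protocol is too mixed to support that.

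The second reply is that the gap is narrow and other provisions would work. Most of this stands too. The death must be related, come after escalation and during accrual, have no recorded Grade 4 stage, and not be in the second Grade 3 patient. The sponsor would know within a day. Section 5.6 says that termination results from its criteria, and a related death is the most severe adverse reaction possible. Yet applying that criterion needs judgement, and it prescribes neither an SMC meeting nor a pause short of termination.

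One might add that some other related event would probably trigger a hold anyway. A probability taken over the whole post-escalation phase does not show this, because a trigger that fires before the death gives no protection after it.

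**Conclusion.** The gap in the wording is real, and it is minor. For a related death without a recorded Grade 4 stage, and not in the second Grade 3 patient, the rule as written gives the wrong result. No other section supplies a mandatory SMC meeting or hold.

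If it happened and no one acted, about 7 further patients at most could start before the next routine meeting. The average is about 1 to 3, or 1.1 to 2.7 with meetings counted from first patient in. These figures rest on even accrual over 91 weeks, 14 post-escalation patients, assumed death timing, and no other trigger or sponsor action. They are conditional on a rare event, and the documents give no basis for its probability.

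A reader might infer that deaths in this trial go unreviewed, or that seven patients would be exposed. The documents support neither. Reporting is prompt, termination is provided for, the SMC would see the death at its next meeting, and seven is the extreme of the timing under total inaction. No analysis or estimate is affected.

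**What to change.** In Section 9.8, insert the words *or 5* after *Grade 4* in the post-escalation trigger, so that one related Grade 4 or Grade 5 event convenes the SMC and holds inclusion. Mirror this in Section 3.0, whose only event-driven meeting at present is for DLT.

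A matching sentence for the escalation phase is optional. The wording there has the same omission, but the six-week stagger and the cohort reviews already limit what could follow.

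The cost is a few words of text and, in conduct, an occasional extra SMC meeting with a short pause in inclusion after a related death. Sample size, endpoints and analyses do not change.

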9.9 Other Safety Considerations

Any significant worsening noted during interim or final physical examinations, electrocardiogram, x-ray filming, any other potential safety assessment required or not required by protocol should also be recorded as a nonserious or serious AE, as appropriate, and reported accordingly.

9.9.1 Evaluating Adverse Events

An Investigator who is a qualified physician will evaluate all adverse events according to the NCI Common Terminology for Adverse Events (CTCAE), version 4.0. Any adverse event which changes CTCAE grade over the course of a given episode will have each change of grade recorded on the adverse event case report forms/worksheets.

All adverse events regardless of CTCAE grade must also be evaluated for seriousness.

9.10 Sponsor Responsibility for Reporting Adverse Events

All Adverse Events will be reported to Competent Authorities and Investigators in accordance with applicable national laws and regulations.

Suspected Unexpected Serious Adverse Reactions (SUSARs) will be reported to the Competent Authority according to national regulation. The following timelines should be followed:

The sponsor will ensure that all relevant information about SUSARs that are fatal or life-threatening is recorded and reported as soon as possible to the Competent Authority concerned in any case no later than seven (7) days after knowledge by the sponsor of such a case, and that relevant follow-up information is subsequently communicated within an additional eight (8) days.

All other SUSARs will be reported to the Competent Authority concerned as soon as possible but within a maximum of fifteen (15) days of first knowledge by the sponsor.

SUSARs will be reported using the CIOMS form since Oslo University Hospital (sponsor) is not connected to EudraVigilance.

10.0 COLLATERAL RESEARCH.

An extensive research program will be conducted. The patient informed consent form will allow for performing biomarker analyses, immunological studies, gene profiling and studies of tumor evolution/heterogeneity during treatment, as well as comparison with data/material from other studies.

10.1 Biobanking:

Please see the study flow chart for information on the time points for collection of biopsies and peripheral blood.

- Tumor biopsies collected pre, during and post therapy (time of progression). If sufficient tissue is available, the tumor will be cut into two/three pieces:
 - Fresh tumor cells/ tumor infiltrating lymphocytes frozen as cell suspension for CYTOF/flow cytometry, analysis of T cell specificity with multimers and functional immune assays
 - Snap-frozen tumor biopsies
 - FFPE tissue
- Peripheral blood samples collected pre-, during and post-therapy:
 - Peripheral blood mononuclear cells, processed with gradient centrifugation and frozen on liquid nitrogen
 - Plasma/serum, separated and frozen.

10.2 Plans for translational research addressing exploratory endpoints

The list below does not represent a mandatory list of assays that are to be performed, but provides an overview of the current plans. The prioritization of assays will be subject to review during the trial. Additional assays may be performed, reflecting ongoing developments in the field. Some of these assays will only be performed on selected patients, due to cost and work load.

1. Gene profiling with selected panels
2. Pathology/immunohistochemistry on all patients (incl. PD-L1, markers for immunogenic cell death and for lymphocyte and macrophage subpopulations)
3. DNA exome seq. of tumor and normal PBMCs on selected patients (mutations, HLA types/loss, SNPs in immune pathways)
4. RNA transcriptome sequencing of tumor on selected patients (gene expression profiles, neoantigens)
5. Serum biomarkers/soluble biopsies, including
 - a. circulating DNA
 - b. circulating micro RNA
 - c. Bioplex cytokine- and MMP panels
6. Characterization of cell suspensions from tumor and peripheral blood:

- a. CYTOF (investigating subpopulations/heterogeneity/evolution, both within tumor cells, immune cells and other stromal cells; relate CYTOF data to gene profiling and mRNA expression)
 - b. Flow cytometry, including the use of panels for regulatory T cells and myeloid suppressor cells(4)
7. Test of T cell reactivity against HPV-antigens, common tumor antigens and the individual spectrum of antigens in each patient's tumor, identified through tumor sequencing/epitope prediction.
 - a. Functional T cell assays, incl. ELISPOT, proliferation, Bioplex cytokine profiling, multimers (5, 6)
8. Tumor gene profiling for investigating tumor evolution/heterogeneity during treatment. Possible validation with mass spectrometry, CyTOF and IHC.

